8. PHARMACEUTICAL INFORMATION

A list of the adverse events and potential risks associated with the investigational or commercial agents administered in this study can be found in Section 10.1.

8.1 CTEP IND Agent

8.1.1 IPdR (NSC 726188)

Chemical Name: 5-iodo-2-pyrimidinone-2'-deoxyribose

Classification: Pyrimidinone nucleoside analog

Molecular Formula: C₉H₁₁IN₂O₄ **M.W.:** 338

Mode of Action:

Oral pro-drug hepatically converted by aldehyde oxidase to IUDR, for IUDR-mediated radiosensitization.

Description:

IPdR drug substance is a light-yellow powder.

How Supplied:

IPdR is supplied by the DCTD, NCI and distributed by the Pharmaceutical Management Branch, CTEP, DCTD, NCI as 75 mg and 600 mg capsules.

- The 600 mg capsules are dark green, opaque, hard gelatin capsules, size 0 and contain the inactive ingredients: microcrystalline cellulose, sodium starch glycolate and magnesium stearate. Capsules are packaged in 60 cc white, high-density polyethylene (HDPE) bottles with induction seals and white child-resistant polypropylene plastic caps. Each bottle contains 30 capsules with a polystyrene coil and a silica gel desiccant.
- The 75 mg capsules are white, opaque, hard gelatin capsules, size 1 and contain the inactive ingredients: microcrystalline cellulose, sodium starch glycolate, and magnesium stearate. Capsules are packaged in 60 cc white, high-density polyethylene (HDPE) bottles with induction seals and white child-resistant polypropylene plastic caps. Each bottle contains 30 capsules with a polystyrene coil and a silica gel desiccant.

Storage:

Store bottles refrigerated at 2°-8°C in the original manufacturer's container. Do not re-package capsules or remove the desiccant.

If a storage temperature excursion is identified, promptly return IPdR capsules to 2°-8°C and quarantine the supplies. Provide a detailed report of the excursion (including documentation of temperature monitoring and duration of the excursion) to [contact] for determination of suitability.

Stability:

Shelf life stability testing of the intact bottles is on-going.

Route and Method of Administration:

Oral. Take by mouth on an empty stomach, either 1 hour before or 2 hours after meals.

Availability

IPdR is an investigational agent supplied to investigators by the Division of Cancer Treatment and Diagnosis (DCTD), NCI.

8.1.2 Agent Ordering and Agent Accountability

8.1.2.1 NCI-supplied agents may be requested by eligible participating Investigators (or their authorized designee) at each participating institution. The CTEP-assigned protocol

number must be used for ordering all CTEP-supplied investigational agents. The eligible participating investigators at each participating institution must be registered with CTEP, DCTD through an annual submission of FDA Form 1572 (Statement of Investigator), NCI Biosketch, Agent Shipment Form, and Financial Disclosure Form (FDF). If there are several participating investigators at one institution, CTEP-supplied investigational agents for the study should be ordered under the name of one lead participating investigator at that institution.

Subjects must be enrolled prior to submission of a Clinical Drug Request via the PMB Online Agent Order Processing (OAOP) application. No starter supplies of IPdR are available.

Submit agent requests through the PMB OAOP application. Access to OAOP requires the establishment of a CTEP Identity and Access Management (IAM) account and the maintenance of an “active” account status, a “current” password, and active person registration status. For questions about drug orders, transfers, returns, or accountability, call or email PMB any time. Refer to the PMB’s website for specific policies and guidelines related to agent management.

8.1.2.2 Agent Inventory Records – The investigator, or a responsible party designated by the investigator, must maintain a careful record of the receipt, dispensing and final disposition of all agents received from the PMB using the appropriate NCI Investigational Agent (Drug) Accountability Record (DARF) available on the CTEP forms page. Store and maintain separate NCI Investigational Agent Accountability Records for each agent, strength, formulation and ordering investigator on this protocol.

8.1.3 Investigator Brochure Availability

The current versions of the IBs for the agents will be accessible to site investigators and research staff through the PMB OAOP application. Access to OAOP requires the establishment of a CTEP IAM account and the maintenance of an “active” account status, a “current” password and active person registration status. Questions about IB access may be directed to the PMB IB Coordinator via email.

8.2 Capecitabine

Product description: Capecitabine is commercially available as 150 mg or 500 mg tablets. Capecitabine tablets should be stored at room temperature (15° to 30°C) in the container in which they are provided. Capecitabine is a white to off-white crystalline powder with an aqueous solubility of 26 mg/mL at 20°C. Capecitabine is supplied as biconvex, oblong film-coated tablets for oral administration. Each light peach-colored tablet contains 150 mg capecitabine and each peach-colored tablet contains 500 mg capecitabine.

Solution preparation: Capecitabine is an oral medication

Route of administration: Capecitabine should be taken by mouth twice daily on days of radiation approximately 12 hours apart, within 30 minutes of a meal with about 200 ml of water

Agent Ordering: Capecitabine is commercially available

Please refer to Capecitabine FDA package insert for complete product information

9. STATISTICAL CONSIDERATIONS

9.1 Study Design/Endpoints

This is a phase 1 study using an accelerated titration design according to Simon *et al.* (Simon *et al.*, 1997). A 100% dose increment will be used in Part IA (single-patient cohorts), and a more conservative dose increment (dose increment adjusted to accommodate availability of 75mg and 600mg IPdR capsules) will be used in Part IB (3+3 cohort). The doses of RT and capecitabine will be identical in Part IA and Part IB. Part IA and Part IB are designed with a stopping rule rather than a pre-specified statistical model (Le Tourneau *et al.*, 2009). As a phase 1 study, the primary objective is to determine the MTD and document the toxicities of once daily PO IPdR when administered with capecitabine (825 mg/m² BID) and RT (50.4 Gy in 28 fractions).

DLT in Part IB will be reached when each of at least two of six patients enrolled at a dose level experience:

- any two grade 3 treatment-related non-hematologic toxicities, OR
- any one grade 4 treatment-related hematologic and/or GI toxicity.

Three additional patients will be treated at the dose level below the dose associated with DLT to establish the MTD. The MTD is defined as the dose below which 2 or more of 6 patients experience DLT attributable to IPdR.

The total of six patients treated at the MTD will suffice to recognize common toxicities; common toxicities at MTD (those occurring in 30% of patients to be treated at the MTD) will rarely be

unobserved ($p=0.117=0.7^6$) and very common toxicities (those occurring in 50% of patients) will almost never be missed ($p=0.016=.5^6$).

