6.2 Definition of Dose-Limiting Toxicity

Management and dose modifications associated with the above AEs are outlined in Section 7.

DLTs will be captured until 4 weeks after completion of IPdR therapy and will be graded according to the CTCAE v5.0. DLTs will be defined as clinically significant grade 3 or 4 toxicities possibly or probably related to study treatment.

- Grade 4 neutropenia (ANC < 500/mm³)
- Grade 4 electrolyte toxicities
- ANC <1000/mm³ with fever (temp >101 F) or infection
- Grade 4 thrombocytopenia: Platelets <25,000/mm³
- Platelets <50,000/mm³ requiring transfusion
- Grade 3 or 4 treatment related non-hematologic toxicities excluding alopecia.
- Patients who receive <67% of intended IPdR secondary to treatment related toxicities will also be considered as having a DLT

In addition, during chemoradiation, DLTs will also include AEs requiring interruptions of radiation for >5 consecutive scheduled fractions (and / or ≥ 9 total scheduled fractions) or for >10 consecutive scheduled doses of capecitabine (and / or ≥ 19 total scheduled doses of capecitabine). The following AEs will not be considered DLTs:

- Any grade of alopecia,
- Grade 3 arthralgia or myalgia,
- Brief (<1 week) grade 3 fatigue,
- Grade 3 fever,

- Grade 3 diarrhea or vomiting responding to supportive care
 - Grade 3 nausea, vomiting or diarrhea will be considered a DLT if it occurs for greater than 48 hours despite maximal medical support.
- Grade 3 radiation dermatitis,
- Grade 3 or 4 electrolyte abnormalities will not be considered DLTs if the electrolyte disorder can be corrected to grade 2 or less within 72 hours.

All patients who have received at least one dose of IPdR are evaluable for toxicities.

For dose escalation decisions, patients should have completed $\geq 80\%$ of the planned chemoradiation doses unless the reason for discontinuation is an AE that qualifies for DLT.

Dose escalation will proceed within each cohort in Part IB according to the following scheme. DLT is defined above.

Number of Patients with DLT at a Given Dose Level	Escalation Decision Rule
0 out of 3	Enter 3 patients at the next dose level.
≥ 2	Dose escalation will be stopped.

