1 out of 3	Enter 3 more patients at this dose level. 
• If 0 of these 3 patients experience DLT, proceed to the next dose level.• If 1 or more of this group suffer DLT (i.e. 2 of 6 patients), then dose escalation is stopped, and this dose is declared the maximally administered dose.
≤ 1 out of 6 at highest dose level below the maximally administered dose	This is generally the recommended phase 2 dose. At least 6 patients must be entered at the recommended phase 2 dose.

During the MTD dose finding portion, patients who are removed from study for reasons other than a DLT will be replaced.

6.3 Dose Expansion Cohorts:

For the expansion cohort, patients will continue to be monitored for occurrence of DLT. Three additional patients will be treated at the dose level below the dose associated with DLT to establish the MTD. The MTD is defined as the dose below which 2 or more of 3 to 6 patients experience DLT. The MTD will be deemed to be RP2D if $\geq 80\%$ of the patients are able to receive $\geq 80\%$ of the planned treatment doses. Monitoring of all safety and toxicity data is done by the Principal Investigator and the Corresponding Organization on a real-time basis as data are entered into Medidata Rave using the Web Reporting Module. All participating sites are expected to notify the Principal Investigator when a DLT has occurred.

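### Section 9.1 states a Part IB DLT and MTD rule that conflicts with Sections 6.2 and 6.3, and no text says which prevails when the MTD is declared

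*Combined protocol and SAP*

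**What the plan says.** Section 6.2 gives the patient-level definition: "DLTs will be defined as clinically significant grade 3 or 4 toxicities possibly or probably related to study treatment". Its list includes "Grade 3 or 4 treatment related non-hematologic toxicities excluding alopecia", so one such event is enough, subject to exceptions listed further down. Those exceptions include grade 3 radiation dermatitis, grade 3 fatigue lasting under a week, and grade 3 diarrhea or vomiting that responds to supportive care. The section then ties Part IB escalation to that definition: "Dose escalation will proceed within each cohort in Part IB according to the following scheme. DLT is defined above". In its decision table, when a second patient among six has a DLT, "then dose escalation is stopped, and this dose is declared the maximally administered dose".

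Section 6.3 follows with an MTD rule: "The MTD is defined as the dose below which 2 or more of 3 to 6 patients experience DLT". It has no limit on attribution.

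Section 9.1, the statistical section, says something else. "DLT in Part IB will be reached when each of at least two of six patients enrolled at a dose level experience" one of two things: "any two grade 3 treatment-related non-hematologic toxicities, OR" one grade 4 treatment-related hematologic and/or GI toxicity. It then states: "The MTD is defined as the dose below which 2 or more of 6 patients experience DLT attributable to IPdR".

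Section 6.1.1 adds a third wording for Part IB. It names grade 3 non-hematopoietic or grade 4 hematopoietic/GI DLT, does not require two events, and does not refer to Section 6.2. The Part IA table in the same section treats one grade 3 non-hematologic toxicity as a DLT and does refer to 6.2 for exceptions.

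**The concern.** The MTD is the first primary objective (Section 1.1), and it depends entirely on which patients are counted as having a DLT. Sections 9.1 and 6.2 differ on how many events a patient needs, which types count, which are excepted and, for the MTD, which agent the event must be attributed to. If the two sections classify the same patients differently, the declared MTD rests on a choice between definitions made after the data are known. The MTD feeds the recommended phase 2 dose (Section 6.3), and the study is meant to inform whether IPdR enters NRG-GI002 as an experimental arm (Section 2.1.4). For single grade 3 non-hematologic events, 9.1 is the less protective of the two rules.

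**Working it through.** **The plan's own figures.** Section 9.1 gives the chance that a toxicity goes unseen in six patients at the MTD: 0.7^6 = 0.1176 (printed as 0.117) and 0.5^6 = 0.0156 (printed as 0.016). Both reproduce. They do not bear on the conflict.

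**The rules side by side.** In both 6.3 and 9.1 I read the MTD sentence as meaning the level below the dose at which two or more patients have a DLT. Taken literally, both sentences put the toxicity below the MTD.

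| Feature | Sections 6.2/6.3 | Section 9.1 |
|---|---|---|
| Grade 3 non-hematologic events needed per patient | One, if clinically significant, related and not excepted | Two |
| Grade 4 event neither hematologic nor GI (e.g. renal) | DLT, apart from electrolyte events corrected to grade 2 or less within 72 hours | Not mentioned |
| Febrile or infected neutropenia below 1,000/mm³; platelets below 50,000/mm³ needing transfusion; under 67% of planned IPdR because of toxicity; long radiation or capecitabine interruptions | DLT | Not mentioned |
| Listed exceptions | Yes | None |
| Attribution for the MTD | Study treatment | IPdR |
| Patients | Two or more of 3 to 6 | Two or more of 6 |

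**Three cases that need no rates.**

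1. Two of six patients each have one clinically significant, related, non-excepted grade 3 non-hematologic event and nothing else. Section 6.2 counts 2 DLTs and escalation stops; 6.3 puts the MTD below this dose. Section 9.1 counts 0, so by its terms DLT has not been reached and it yields no MTD at that point.
2. A level has been expanded to six because the level above was stopped. Two of the six each have grade 3 radiation dermatitis and brief grade 3 fatigue, both judged related to treatment and attributable to IPdR. Section 6.2 counts 0 of 6, so this level stands as the MTD under 6.3. Section 9.1 has no exceptions, so both patients meet it, DLT is reached here, and the MTD moves lower.
3. Two of six patients each have grade 4 diarrhea attributed to capecitabine alone. Section 6.2 counts 2 DLTs (its diarrhea exception covers grade 3 only) and 6.3 puts the MTD below this dose. The 9.1 MTD sentence counts 0, because neither event is attributed to IPdR.

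Cases 2 and 3 give different MTD results from the same data. Case 1 sets a section that answers beside one that does not.

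**Illustration only.** Suppose six patients are treated at a dose, and let p be the chance that a patient meets the rule in question. Then

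P(at least 2 of 6) = 1 − (1−p)^6 − 6p(1−p)^5.

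For 6.2/6.3, take p as the share of patients with at least one qualifying grade 3 non-hematologic event. I assume 30%. Section 9.4.1 uses 30% as a target prevalence for all grade 3/4 toxicity, and 9.1 uses it for a common toxicity at the MTD; neither is this quantity. The result is 1 − 0.1176 − 0.3025 = 0.580.

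For 9.1, p = 0.30 × s, where s is the share of those patients who have a second such event. The documents do not give s.

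| s | p under 9.1 | P(at least 2 of 6) |
|---|---|---|
| 0% | 0 | 0% |
| 25% | 0.075 | 7% |
| 50% | 0.150 | 22% |
| 75% | 0.225 | 41% |
| 100% | 0.300 | 58% |

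With a 20% base rate the comparison is 34% under 6.2/6.3 against 0% to 34% under 9.1 (11% at s = 50%). With 40% it is 77% against 0% to 77% (34% at s = 50%). Grade 4 events and patients with only excepted events are left out.

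**The case against.** The strongest reply is that Chapter 6 is complete in itself. Section 6.2 defines a DLT and ties Part IB escalation to that definition. Its table stops escalation, names the maximally administered dose and points to the recommended phase 2 dose; 6.3 then gives the MTD. Section 13.1 adds Principal Investigator sign-off on every dose decision and calls at least monthly with the CTEP Medical Officer(s). A team following the treatment plan is not left without a rule. This stands, and it lowers the severity.

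A reader might go further and infer that 9.1 must control, because the Schema and Section 6.1.1 enter cohorts until DLT is reached and 9.1 is where that phrase is spelled out. The documents do not support this: neither place cites 9.1, and the 6.2 table gives the phrase a working meaning. Nor does 9.1 restart escalation once 6.2 has stopped it, so the text does not show that patients would be escalated past a dose 6.2 rejects.

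A reader might also take 58% against 22% as the size of the error. It is not: the 9.1 figure runs from total difference to no difference as s goes from 0% to 100%. It also conditions on six patients being treated, whereas a 3+3 cohort can stop or move on after three. Under the full 6.2 scheme at p = 0.30, the chance of stopping at that level is 1 − [0.7^3 + 3(0.3)(0.7^2)(0.7^3)] = 0.51.

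Finally, counting only IPdR-attributed events toward the MTD could be deliberate, since capecitabine and radiation start at fixed doses. That is possible, but then 6.2 and 6.3 should say the same, and they do not.

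**Conclusion.** Sections 9.1 and 6.2/6.3 contradict each other on the event rule and attribution that determine the primary endpoint, and no text ranks them when the MTD is declared. In practice 6.2 and 6.3 would probably be used, so this should be corrected but does not leave the trial unworkable. The contradiction can change the declared MTD in either direction: case 2 lowers it under 9.1, and case 3 removes the events that would have placed it lower. This rests on the plain wording, on reading no 6.2 exceptions into 9.1 (which does not refer to them), and, for case 1, on both events being judged clinically significant. How often the rules would disagree cannot be estimated from the documents.

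**What to change.** In Section 9.1, replace the two DLT bullets, their lead-in and the MTD sentence with: *DLT is as defined in Section 6.2. The MTD is the highest dose level at which at most 1 of 6 patients has a DLT; the RP2D is then determined as in Section 6.3.* Make the MTD sentence in 6.3 match, and keep its 80%/80% delivery test for the RP2D. Point the Part IB sentence in 6.1.1 to the 6.2 definition.

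This drops the restriction to IPdR-attributed events, so that attribution follows 6.2. If the sponsor does intend an IPdR-only rule, it should be stated identically in 6.2, 6.3 and 9.1.

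The cost is a protocol wording amendment, with no added patients or procedures.

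### Section 9.1's chances of missing a toxicity at the MTD (0.7^6 and 0.5^6) do not hold for toxicities that are dose-limiting whenever they occur; given how the MTD is chosen, those chances are at least 28% and 14%

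*Combined protocol and SAP*

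**What the plan says.** Section 9.1 states that "The total of six patients treated at the MTD will suffice to recognize common toxicities" and supports this with two probabilities:

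- "common toxicities at MTD (those occurring in 30% of patients to be treated at the MTD) will rarely be" unobserved, with a probability of 0.117 given as 0.7^6.
- "very common toxicities (those occurring in 50% of patients) will almost never be missed", with a probability of 0.016 given as 0.5^6.

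Neither statement is restricted to a class or grade of toxicity.

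The choice of dose depends on the DLT count in the same patients. The escalation table in section 6.2 describes the dose normally recommended for phase 2 as the one with "≤ 1 out of 6 at highest dose level below the maximally administered dose", and adds that "At least 6 patients must be entered at the recommended phase 2 dose". If an expanded cohort reaches 2 of 6, "then dose escalation is stopped, and this dose is declared the maximally administered dose". Section 9.1 puts it this way: "The MTD is defined as the dose below which 2 or more of 6 patients experience DLT attributable to IPdR". That sentence is awkward, but the table makes the workable reading clear: the dose kept has at most 1 of 6 patients with DLT.

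**The concern.** The figures 0.7^6 and 0.5^6 treat the six patients as an unselected sample. For a toxicity that always counts as a DLT they are not: a dose at which 2 to 6 of the six had it is never called the MTD. The binomial calculation counts those outcomes as detections, although they cannot occur at a dose that carries the label. The chance of having seen nothing, among doses that do carry it, is therefore larger than printed.

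This is the only quantitative statement the plan offers for six patients at the MTD. Section 9.2 says only that the sample size is whatever is needed to establish the MTD. Section 2.1.4 says the results will inform whether IPdR is suitable as an experimental arm of NRG-GI002. A reader who applies the section 9.1 assurance to severe toxicities would take more comfort from a clean cohort of six than the design provides.

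**Working it through.** **Inputs.** Six patients at the MTD, and true rates p of 30% and 50% (section 9.1). A dose is kept only with at most 1 of 6 DLTs (table in 6.2; MTD sentence in 9.1).

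**1. The plan's own figures.** P(0 of 6) = (1 − p)^6.

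- p = 0.30: 0.7^6 = 0.1176. The printed 0.117 is truncated, which is immaterial.
- p = 0.50: 0.5^6 = 0.0156, printed as 0.016.

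Both reproduce.

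**2. Condition on selection, for a toxicity that is a DLT whenever it occurs, with no other DLTs.** A single DLT may fall in any of the six positions: 1 of 3 then 0 of 3, or 0 of 3 then 1 of 3 on expansion. So P(at most 1 of 6) = (1 − p)^6 + 6p(1 − p)^5, and

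P(0 of 6 | at most 1 of 6) = (1 − p)/(1 + 5p).

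| True rate | P(0 of 6) | P(exactly 1 of 6) | P(at most 1 of 6) | P(0 given at most 1) |
|---|---|---|---|---|
| 30% | 0.1176 | 0.3025 | 0.4202 | 0.280 |
| 50% | 0.0156 | 0.0938 | 0.1094 | 0.143 |

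The ratios to the plan's figures are 0.280/0.1176 = 2.4 and 0.143/0.0156 = 9. A simulation of the whole 3+3 path, including expansion of the lower dose, gave about 28.1% and 14.3 to 14.4%, whichever DLT rate was assumed for the next dose (40% or 60% in the first case, 60% or 80% in the second).

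**3. Why these are minima for such a toxicity.** Let a further share s of patients have only other DLTs. The miss probability becomes (1 − p + 5s)/(1 + 5p + 5s), which rises with s.

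- p = 0.30, s = 0.10 (assumed): 1.2/3.0 = 40%.
- p = 0.50, s = 0.10 (assumed): 1.0/4.0 = 25%.

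**4. Toxicities that are only sometimes dose-limiting.** Suppose a toxicity occurs in a share p of patients and is dose-limiting in a share d of all patients, with no other DLTs. Zero occurrences imply zero DLTs, so the miss probability is (1 − p)^6 divided by P(at most 1 of 6 at rate d). The values of d are assumptions.

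- p = 0.30, d = 0.10: 0.1176/0.8857 = 13.3%.
- p = 0.30, d = 0.15: 0.1176/0.7765 = 15.2%.
- p = 0.50, d = 0.10: 0.0156/0.8857 = 1.8%.

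Setting d = 0 returns the plan's figure, and d = p returns the figure in step 2.

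**The case against.** The strongest reply is that the sentence concerns toxicities, not DLTs. It fits objective 1.1.2, which is to determine the CTCAE toxicities of the combination, and a toxicity can be recognized at any grade. Section 6.2 also excludes several severe events from DLT: grade 3 fever, arthralgia or myalgia, radiation dermatitis, brief fatigue, and diarrhea or vomiting that responds to supportive care. For much of what the sentence covers, the printed figures are right or nearly so, as step 4 shows. This stands and sets the scope of the point. It does not rescue the sentence for DLTs, because section 9.1 draws no such line.

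Second, 0 of 6 always passes the rule, so 0.7^6 and 0.5^6 are also the joint probability that six patients show no DLT and the dose is kept. That is true. But the sentence speaks of toxicities at the MTD, that is, at a dose already selected, and the conditional probability answers that statement.

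Third, a dose with a 50% DLT rate would seldom be kept. It passes the at-most-1-of-6 rule 10.9% of the time, so the 14% describes an uncommon situation. A dose with a 30% DLT rate passes 42% of the time, which is not uncommon.

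Fourth, when escalation stops for DLT, at least two have been seen at the next dose, so a dose-related toxicity may already be known from there. Monitoring for DLT also continues in the expansion cohort. Both facts soften the practical consequence. Neither changes the probability for the six patients to which the sentence refers.

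A reader might go further and infer that section 9.1 is miscalculated, or that 28% and 14% apply to every toxicity. The documents support neither: the binomial arithmetic reproduces, and the higher figures apply only when every occurrence is a DLT.

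**Conclusion.** As worded, section 9.1 claims too much for dose-limiting toxicities. For a toxicity that is a DLT whenever it occurs, the chance that none was seen in the six patients, given that the dose was kept as the MTD, is at least 28% at a true rate of 30% and at least 14% at 50%. The plan gives 11.7% and 1.6%. For toxicities that are not DLTs and are independent of DLTs, the plan's figures stand. Toxicities that are sometimes dose-limiting lie between when there are no other DLTs.

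The result rests on the at-most-1-of-6 rule, on independent patients with a common true rate, and on exactly six patients at the dose. Which events it covers cannot be settled from the documents. Section 9.1 requires two grade 3 non-hematologic toxicities or one grade 4 hematologic or GI toxicity per patient, and attributes the DLTs in its MTD sentence to IPdR. Section 6.2 counts grade 3 or 4 toxicities related to study treatment, with listed exceptions. The two must be reconciled; the arithmetic is the same either way.

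It would be tempting to conclude that the escalation rule or the cohort size is unsound. That does not follow: six comes from the 3+3 rule, which section 9.1 describes as a stopping rule and not a statistical model, and no decision depends on the two probabilities.

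**What to change.** Revise the closing paragraph of section 9.1 to:

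- limit 0.118 and 0.016 to toxicities that do not count as DLTs and are independent of DLTs;
- state that for a toxicity that is dose-limiting whenever it occurs, the probability of observing none in six patients, given that the dose was declared the MTD, is at least 0.28 (true rate 30%) and at least 0.14 (true rate 50%);
- remove, for DLTs, the claims that six patients are enough and that very common events would hardly ever be missed;
- say that the events these figures cover depend on reconciling the DLT definitions in 6.2 and 9.1.

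If the DLT rate at the MTD is reported with an exact 95% confidence interval (0 to 46% for 0 of 6; 0.4 to 64% for 1 of 6), note that the interval assumes a fixed sample and does not account for selecting the dose on the same six patients.

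The cost is wording alone, apart from the separate work of reconciling the definitions. The stated assurance becomes less favourable.
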